8.1.6 STUDY PROCEDURES

Tests to assess efficacy:

Gastric Emptying Scintigraphy (GES)

Gastric emptying scintigraphy will be performed using a low-fat, egg white Eggbeaters[®] meal with imaging at 0, 1, 2, 4 hours after meal ingestion, as endorsed by the Society of Nuclear Medicine and American Neurogastroenterology and Motility Society (ANMS) (34,35). This protocol ensures standardized information about gastric emptying across multiple sites. Participants are instructed to come to the Nuclear Medicine Section in the morning after an 8-hour overnight fast, that is nothing by mouth after midnight and narcotic free for the 3-days prior to the scheduled test. The morning of the week-4 GES test, the participant will wait to take their buspirone until thirty minutes *prior to the start of the GES test*. If the participant normally takes insulin, then they should take one-half of their normal long-acting insulin dose prior to the visit. All diabetics will have their glucose checked prior to starting the GES test, with appropriate treatment measures being taken if low blood sugar (hypoglycemia or glucose < 60 mg/dL) or high blood sugar (hyperglycemia or glucose >270 mg/dL) is detected. GES is performed using a standard low-fat, egg-white Eggbeaters[®] meal to measure solid emptying. The meal consists of the equivalent of two large eggs radiolabeled with 0.5-1 mCi Tc-99m sulfur colloid served with two pieces of white bread and jelly. Participants are given 120 ml water. Following ingestion of the meal, imaging is performed at 0, 1, 2 and 4 hrs with the participant upright for measuring gastric emptying of Tc-labeled solids. In between imaging, participants generally sit in the nuclear medicine waiting area. Symptoms (nausea, fullness, pain severity, and episodes of vomiting) will be monitored and recorded during the GES test. Gastric emptying is analyzed as percent of radioactivity retained in the stomach over time using the geometric center of the decay-corrected anterior and posterior counts for each time point. Gastric retention of Tc-99m >60 % at 2-hours and/or >10% at 4-hours is considered delayed gastric emptying of solids. Delayed gastric emptying is graded according to the gastric retention at 4-hours: mild (<20% gastric retention at 4 hours), moderate (>20 to 35%), and severe (>35%) [35].

Intragastric meal distribution (IMD), as an assessment of fundic accommodation (FA), during GES.

Analysis of regional intragastric meal distribution will be performed of the digital archived gastric emptying images, both at baseline and at the 4-week visit. We will use a modification of the method reported by Piessevaux, Tack, et al to assess intragastric meal distribution [14]. We will use our semi-automated analysis of regional intragastric meal distribution during GES. The analysis begins by aligning the images, then drawing regions of interest around the stomach using thresholding. The longitudinal axis of the stomach is then constructed. The stomach is then divided into two (proximal, distal) regions of interest by finding the midpoint of the longitudinal axis. The amount of radioactivity in each gastric region will be expressed as a percent of the total amount of radioactivity in the stomach at time 0. This will be assessed over time. The ratio of proximal over distal counts will be computed for each time period (0, 1, 2, 4 hours). The amount in the proximal region of interest at time 0

provides a measure of fundic accommodation. Impaired fundic accommodation using IMD is <0.568 ratio of the proximal gastric counts to the total gastric counts.

Electrogastrogram (EGG) with water load satiety test [36]:

For each EGG and water load test, the clinical center needs to have a one-liter opaque cup for water, 3 EGG leads, a dedicated quiet area for the EGG recording, a reclining chair, a blanket and the 3CPM EGG equipment and software. In addition, if the participant normally takes insulin, then they should take one-half of their normal long-acting insulin dose prior to the visit. The morning of the week-4 EGG, the participant will wait to take their buspirone dose *until 15 minutes before the baseline EGG*.

On the morning of the EGG and water load satiety test, the participant will arrive at the center after an 8-hour fast, that is nothing by mouth after midnight. Participants may take their usual medications with a small amount of water (up to 4 ounces) up to two hours prior to the study, but should refrain from coffee, tea, or juice. After arriving at the clinic, diabetic participants' blood glucose level will be checked to ensure it is less than 270 mg/dL. If the participant's blood glucose level is greater than 270 mg/dL, it is either treated and rechecked before proceeding or the EGG and water load satiety test will be rescheduled for another day under better glucose control. The participant will take their buspirone dose fifteen minutes prior to the 4-week baseline EGG recording. Baseline symptoms prior to EGG recording will be obtained using visual analog scales for stomach fullness, hunger, nausea, bloating, and abdominal discomfort. The subject will mark each symptom scale with a vertical line to indicate how they currently feel in terms of that symptom's severity on a score from 0 (no symptoms) to 100 (the most severe symptoms). Once the EGG and respiratory signals are stable, the baseline EGG recording period can begin. Participants will undergo a 15-minute baseline EGG in a reclining chair with the subject positioned at a 30-45 degree tilt. Participants will then begin the water load satiety test. For this, participants will sit upright. During the test, participants will drink cool water from the 1-liter cup. They will drink for a 5-minute period until they feel "**completely full**." It is important that the research associate at each site gives every participant the same instructions as follows:

"I want you to drink water from this container until you feel **completely full**. You have **up to five minutes** to reach the feeling of **being** completely full. You may stop at any time, up to the five-minute time limit, when you feel completely full. This is not a test to see how much you can drink, but to drink until you **feel you are completely full** in the five-minute period. Do you have any questions about this?"

The total volume of water consumed in mL will be recorded.

A continuous 30-minute EGG recording is then obtained. The participant's symptoms are recorded using a visual analog scale at 10, 20, and 30 minutes after ingestion of the water (at the end of the 0-10 minute, 11-20 minute, and the 21-30 minute periods after the water load ingestion (post-satiety periods)). The test is completed after the 30-minute recording period and the electrodes are removed.

Specimen repositories

Specimens will be collected and stored in the NIDDK Biosample Repository for use as approved by the Steering Committee of the GpCRC and the NIDDK Central Repository after a specified period of time. Specimens include serum and plasma. The blood collected during screening, and at the 4 and 6-week follow-up visits will be separated into plasma and serum, and divided into 0.5 mL aliquots. Aliquots will be kept in a storage facility at -70 to -80 degrees Centigrade until they are shipped on dry ice to the NIDDK Biosample Repository at Precision Medicine.

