Blood drawing: Blood draw may cause mild discomfort, such as swelling, temporary sensation of pain, burning, or a bruise that may develop and last for a few days. Less common risks include a blood clot at the site of puncture, swelling of the vein and surrounding tissues, and possible bleeding from the puncture site. Very rarely, fainting, blood clots or an infection at the site can occur. During the entire study period (up to 14 weeks), subjects will have approximately 6 tablespoons of blood drawn (88 mL) (see section [12.2](#)).

Electrogastrogram (EGG) with water load satiety test: EGG testing involves placement of EGG electrodes on the abdominal skin. An EGG will be performed twice: during screening and at 4 weeks. There may be some soreness in removing the EGG electrodes. During the water load test, the participant drinks water until they are full. Diabetics will have their glucose checked at the beginning and the end of the tests, with appropriate measures being taken if hypoglycemia or hyperglycemia is detected. In addition, each of these two EGG tests will be performed on different days than each of the Gastric Emptying Scintigraphy tests, which may cause inconvenience to the participant.

Gastric emptying scintigraphy (GES) test: A GES test will be performed twice: during screening and at 4 weeks. The total radiation dose for the administration of 0.5-1 microcuries (mCi) 99m-Tc sulfur colloid for one GES test is an Effective Dose Equivalent of 37-53 millirem (adult male and adult female, respectively). The internal organ or tissue receiving the highest radiation dose is the upper large intestine, which will receive 215 millirad. The total

radiation dose for the 0.5-1 mCi administration of 99m-Tc sulfur colloid for the two GES tests included in BESST is an Effective Dose Equivalent of 74-106 millirem. The annual average background value that an individual receives in the United States is 300 millirem. The internal organ or tissue receiving the highest radiation dose is the upper large intestine, which will receive 430 millirad total during BESST. A urine pregnancy test is obtained at study screening and at each visit during study treatment to ensure female participants of child-bearing potential are not pregnant when exposed to radiation or while taking study drug.

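### The risk section says diabetics' glucose is checked before and after the EGG tests for low and high values; the EGG procedure in 8.1.6 has one arrival check, against an upper limit only

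*Combined protocol and SAP*

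**What the plan says.** Section 2.3.1, in the paragraph on the EGG with water load satiety test, states: "Diabetics will have their glucose checked at the beginning and the end of the tests". The action in both directions is stated in the same sentence: "with appropriate measures being taken if hypoglycemia or hyperglycemia is detected". It gives no numerical limits. The same paragraph says each participant has two EGG tests, one in screening and one at 4 weeks.

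Section 8.1.6 holds the procedure. In its EGG text, the participant fasts for 8 hours with nothing by mouth after midnight, and "if the participant normally takes insulin, then they should take one-half of their normal long-acting insulin dose prior to the visit". After arrival, a diabetic participant's "blood glucose level will be checked to ensure it is less than 270 mg/dL". If the value is above 270 mg/dL, "it is either treated and rechecked before proceeding", or the test is moved to another day. The text then covers the baseline recording, the water load and the 30-minute recording, and ends with removal of the electrodes.

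The GES text in 8.1.6 is worded differently: "All diabetics will have their glucose checked prior to starting the GES test", with treatment measures if "low blood sugar (hypoglycemia or glucose < 60 mg/dL) or high blood sugar (hyperglycemia or glucose >270 mg/dL) is detected".

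**The concern.** The risk section describes a safeguard with two time points and two directions. The procedure for the same test contains one routine time point and one direction. A site can follow the 8.1.6 EGG text to the letter and still not do what 2.3.1 says is done.

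The missing half matters for safety. An insulin-treated participant who has fasted overnight and taken a reduced long-acting dose is given only water. The predictable concern is a low value as well as a high one, and the EGG text addresses only the high one. The GES text in the same section has the same fast and the same insulin instruction and names both directions, so the omission looks unintended.

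At stake are participant safety and the accuracy of the risk description, not the efficacy result.

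**Working it through.** The plan states no figure on this point to reproduce. The check is a comparison of texts, followed by a rough count.

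**1. The three statements side by side**

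| | When glucose is checked | Values that trigger action |
|---|---|---|
| 2.3.1, EGG paragraph | Beginning and end | Low and high; no limits given |
| 8.1.6, EGG | Arrival | High only (270 mg/dL) |
| 8.1.6, GES | Before the start | Low (<60 mg/dL) and high (>270 mg/dL) |

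**2. Does the recheck supply the end reading?** No. It follows treatment of a high value and takes place before the test begins.

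**3. Does another section supply it?**

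- Schedule of Activities (1.3): no row for a glucose reading at the time of a test. The metabolic panel includes glucose, but it is a laboratory draw.
- Follow-up visits (8.1.4): the week 4 metabolic panel is listed under the GES day. The EGG day, which is separate, lists no blood draw.
- Safety assessments (8.2): abnormal laboratory values are managed by the site investigator, but the specific repeat rule applies to elevated glucose.
- Management of comorbid conditions (8.2): diabetes is managed by best clinical practice. No reading, time point or low-value trigger is set.
- The EGG text in 8.1.6 does not refer to an operating procedure for glucose checks.

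**4. Time without a reading.** From the EGG text: 15 minutes of baseline recording + up to 5 minutes of drinking + 30 minutes of recording = up to 50 minutes, plus set-up, after an overnight fast.

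**5. How many tests?** The documents do not give the expected number of diabetic participants, so a share is assumed. Tests = share × 108 participants × 2 EGG tests.

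- 20%: 0.20 × 108 = 21.6 participants; × 2 = about 43 tests.
- Registry cohort in 2.2 (54 diabetic of 165): 54/165 = 32.7%; 0.327 × 108 = about 35 participants; × 2 = about 70 tests.
- 50%: 0.50 × 108 = 54 participants; × 2 = 108 tests.

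These are tests conducted in diabetics, not expected low readings. The insulin-treated share is not given, and the registry figure comes from patients with gastroparesis, whereas this trial also admits normal gastric emptying. The contradiction does not depend on the count.

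**The case against.** The strongest reply is that this is an incomplete paragraph rather than an absent safeguard. Section 2.3.1 is part of the same protocol and says the checks will be made. Section 8.2 requires diabetes to be managed by best clinical practice. The EGG text is silent on low values; it does not tell staff to proceed. This stands in part: a reader should not infer that a low arrival value would be ignored, because clinicians may well act on it. What remains is that the written EGG procedure does not call for that action, and that a value nobody measures at the end cannot be acted on.

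Two stronger readings are tempting and are not supported.

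- That the GES procedure also contradicts 2.3.1 because it has no end check. The glucose sentence sits in the EGG paragraph, and the next sentence speaks of the two EGG tests, so the tests meant are most naturally those. The GES has its own paragraph in 2.3.1, which makes no glucose statement, and its procedure already names low and high values before the start. GES participants also eat a meal. There is a conflict only if the sentence is meant to cover both kinds of test, which the text leaves unclear.
- That low values would be missing from the adverse event record. Section 8.3.4 requires all adverse events during the study to be documented, whatever their relationship to treatment. The 8.1.6 wording creates no exemption. Only a low value that is never measured could be missed.

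It is also fair to say that the EGG measures are exploratory or ancillary outcomes.

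**Conclusion.** The contradiction holds for the EGG. The risk section and the EGG procedure differ both on when glucose is checked and on whether a low value triggers action, and no other section closes the gap. It does not extend to the GES as written, nor to adverse event recording.

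The size is modest. On the assumed diabetic share it concerns roughly 43 to 108 EGG tests across the trial, of which an unknown part are in insulin-treated participants. The sample size and the primary analysis are untouched. It should still be corrected, because it bears on participant safety and is cheap to put right.

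**What to change.** Reconcile section 2.3.1 with the EGG procedure in 8.1.6 so that both state the same check times and the same directions, low and high, that trigger action. If the statement in 2.3.1 is what is intended, the EGG procedure needs the end reading and the low-value action that 2.3.1 describes. If it is not, 2.3.1 needs correcting. In the same edit, state in 2.3.1 whether the sentence also covers the GES. If it does, the GES text needs aligning on timing. The clinical limits and the action taken are for the investigators to decide.

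The cost is a protocol wording change and perhaps a glucose field on the EGG form. If the end reading is kept, it adds one glucose check per EGG test in diabetics, which 2.3.1 already describes.

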8.2 SAFETY AND OTHER ASSESSMENTS

Assessments for Safety

- **Physical examination** (e.g., height, weight, waist measurements, vital signs (temperature, heart rate, respiratory rate, blood pressure, ECG).
- **Laboratory results** – All labs including creatinine, ALT, and glucose will be monitored at sites and in the central database and all abnormal values will be managed by the site investigator. If the ALT, creatinine, or glucose levels are elevated, that measure will be repeated within 5 days. If necessary, the participant will be given management advice and information will be provided to the participant's PCP.
- **Standardized Questionnaires:**
 - a. **Symptom side effects:** Participants will be asked if they experienced any side effects from the BESST drug treatment and to describe any side effects. The baseline and follow-up medical histories will inquire about symptoms that may be attributed as side effects of buspirone using a standard set of questions. These symptoms include: headache, dizziness, tiredness, drowsiness, sleep problems (insomnia), nausea, upset stomach, blurred vision, nervousness or excitement.
 - b. **Adverse Event Report form:** This form will document occurrence of an adverse event that threatens the integrity of the BESST trial or the well-being of a study participant during the trial.
 - c. **Serious Adverse Event/IND Safety Report:** This form will document occurrence of any event reported on the Adverse Event Report form that satisfies the FDA expedited IND Safety Report requirement.

- **Biological specimen collection and laboratory evaluations are included in the Schedule of Activities and section in 12.2.** Instructions for the preparation, handling, storage, and shipment of specimens are detailed in the BESST Standard Operating Procedures manual.

If a participant has scores on the psychological questionnaire indicating significant anxiety or depression (HADS-A ≥ 15 and/or HADS-D ≥ 15 indicating severe symptoms) or by the clinician's assessment, the clinical center investigator or staff will suggest that they see a clinical psychologist or psychiatrist and information on these referrals will be given to the participant [37]. If the clinician is concerned that a participant is actively suicidal or at risk of self-harm, the clinical center investigator will help make arrangements for them to be seen that day for further assessment.

For assessment of study intervention adherence see Study Intervention Compliance, [section 6.4](#).

Management of Comorbid Conditions

Any participant's comorbid conditions, including diabetes, will be managed according to the best clinical practice or evidence-based practices by the site principal investigator with input from the participant's primary care physician (PCP), and with consideration for medications contraindicated for use with buspirone (listed in [section 6.5](#)). Most of the comorbid conditions will be treated by continuing the treatments already instituted by the participant's regular physicians; worsening of the condition will be treated by the PI according to best clinical practice along with the participant's regular physicians. If the physician determines that the participant's safety is at risk, the participant's study drug will be discontinued. For follow-up care, the physician will refer the participant to their PCP or a specialist, if needed, and also continue to follow the participant at the site.

A uniform set of practices to be applied by the GpCRC investigators in the care of these participants will be provided in the trial SOP (Standard of Care document), prepared by the GpCRC Steering Committee, including the

Study Medical Safety Officer, and in conjunction with the BESST PI. This document is based on accepted best clinical practice and guidelines from the American Gastroenterological Association, the American Neurogastroenterology and Motility Society, and the American College of Gastroenterology.

If a participant develops diabetes during the participant's participation in the trial and the physician determines the need for antidiabetic medication (e.g., because of lack of response to life style changes), the use of medications not contraindicated with buspirone will be recommended for the specialist to consider. Likewise, for other classes of drugs (anti-hypertensives or anti-depressants) that may be prescribed for a worsening comorbid condition, careful consideration must be given to whether there is a non-contraindicated treatment with buspirone that can be prescribed to the participant, with the ultimate decision being the participant's safety.

Pregnancy will be managed according to the guidelines and study drug will be discontinued immediately upon discovery. For safety, a pregnancy test is done for female participants of child-bearing potential at each follow-up visit and before each GES procedure. In the event of major dermatological reactions such as generalized urticaria, bullous rashes, and exfoliative dermatitis, study drug will be discontinued immediately and not restarted. For local skin reactions, study drug may be discontinued if the skin reactions are potentially drug related. If the rashes clear, the study drug may be restarted.

Monitoring for comorbid conditions is done at each study visit through a follow-up medical history, follow-up physical exam, follow-up adverse event reports, and laboratory measures of glucose or other labs, as well as assessments of vital signs.

In addition to the medications listed in [section 6.5](#), which are exclusionary for the BESST trial, the Buspirone Investigator's Brochure does not recommend use of the drug in patients with impaired hepatic or renal function. Prospective participants with these conditions will be excluded from the trial. Most adverse events reported while taking buspirone are infrequent to rare, and are unexpected in the 4-weeks of treatment in the BESST trial.

Follow-up of Ongoing Adverse Events

Provisions for follow-up of adverse events (AE) include phone calls by the coordinators to assess symptoms, in-person follow up exams when needed to assess vital signs and physical findings and referral to local ongoing care by the PCP or hospital when needed.

The participant is queried about the adverse event until there has been a resolution of the AE. All information is recorded on the Adverse Event Report form and reviewed by the DSMB twice a year or at more frequent intervals if the DSMB determines the need. In addition, any AE with a severity grade greater than 2 is reviewed by the BESST Medical Safety Officer as soon as the event is keyed to the data system.

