1.3 SCHEDULE OF ACTIVITIES (SOA)

Assessment/Procedure	Screening visits	Follow-up visits-Weeks from Randomization			
		RZ	F02	F04*	F06
Consent, HIPAA authorization, demographics	X
Baseline medical history	X
Follow-up medical history	.	.	X	X	X
Side effects survey	X	.	X	X	X
Review for adverse effects	.	.	X	X	X
Review for concomitant medications	X	X	X	X	X
Hospital anxiety and depression (HADS)	X	.	X	X	X
SF-36v2 Quality of life	X	.	.	X	.
PAGI-SYM questionnaire (includes the GCSI)	X	.	X	X	X
Gastrointestinal Symptom Rating Scale (GSRS)	X	.	.	X	X
PAGI-QOL questionnaire	X	.	.	X	X
Patient Health Questionnaire (PHQ-15)	X	.	.	X	.
Clinical Patient Grading Assessment Scale (CPGAS)		.	X	X	X
Detailed (D) or focused (F) physical exam	D	F	F	D	D
Gastric emptying Scintigraphy (GES) test	X	.	.	X	.
Electrogastrogram (EGG) with water load test*	X	.	.	X	.
Provide supplies of GCSI-DD	X	X	X	X	.
Collection of participant's completed GCSI-DD	.	X	X	X	X
Standard of care materials provided	.	X	.	.	.
Eligibility confirmation	X	X	.	.	.
Study drug dispensing	.	X	.	.	.
Review of study drug adherence	.	.	X	X	.
Labs:					
Complete blood count (CBC)	X	.	.	X	X
Comprehensive metabolic panel (CMP)	X	.	.	X	X
Thyroid stimulating hormone (TSH)	X
Fasting HbA1c	X
Pregnancy test	X	X	X	X	.
Banking: Fasting serum and plasma	X	.	.	X	X
Complete Case Report Forms (CRFs)	X	X	X	X	X
Closeout form					

Detailed physical exam (D): anthropometric assessments (body weight [kg], body height [m], waist circumference [cm], and hip circumference [cm]); vital signs (temperature, heart rate, respiratory rate, blood pressure), organ systems chest, lungs, heart, abdomen, liver and spleen, nervous), resting electrocardiogram (ECG)

Focused physical exam (F): anthropometric assessments (body weight [kg], body height [m], waist circumference [cm], and hip circumference [cm]); vital signs (temperature, heart rate, respiratory rate, blood pressure)

Complete blood count (CBC): concentration of white blood cells (WBC), red blood cells, hemoglobin, hematocrit, platelet count

Comprehensive metabolic panel (CMP): glucose, calcium, sodium, potassium, CO₂ (carbon dioxide/bicarbonate), chloride, blood urea nitrogen (BUN), creatinine, total protein, albumin, total bilirubin, alkaline phosphatase (ALP), aspartate aminotransferase (AST), alanine aminotransferase (ALT)

Thyroid Stimulating Hormone test (TSH)

*The EGG with water load test is scheduled for a separate day than the GES testing at Screening and F04 week visits.

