5.2 EXCLUSION CRITERIA

An individual who meets any of the following criteria will be excluded from participation in this study:

- Post-surgical gastroparesis, including prior pyloromyotomy, pyloric resection, vagotomy, bariatric surgery or post-Nissen fundoplication
- Another active disorder which could explain symptoms in the opinion of the investigator
- Concurrent use of opiate narcotic analgesics more than 3 days per week
- Significant hepatic injury as defined by alanine aminotransferase (ALT) elevation of greater than 2xULN or a Child-Pugh score of 10 or greater
- History of significant cardiac disorders (prior heart attack, prior stroke, unstable angina) or significant cardiac arrhythmias or ECG abnormalities defined as history of, or current, arrhythmias including ventricular tachycardia, ventricular fibrillation and Torsade des Pointes and/or prolonged QTc on ECG (>450 msec for men and >470 for women)
- History of chronic kidney disease or on hemodialysis or peritoneal dialysis
- Impaired renal function as defined by estimated glomerular filtration rate (eGFR) $< 60 \text{ ml/min}/1.73^2$ using the [Chronic Kidney Disease Epidemiology Collaboration \(CKD-EPI\) calculator](#)
- Uncontrolled diabetes defined as HbA1c (%) of 10% or more within 60 days of enrollment
- Allergy to buspirone
- Concurrent or prior use (within 30 days) of monoamine oxidase (MAO) inhibitors
- Concurrent or prior use (within 30 days) of benzodiazepines
- Concurrent or prior use (within 30 days) of buspirone, warfarin, haloperidol, and drugs to treat seizures (e.g., phenytoin and carbamazepine)
- For women of child-bearing potential, either pregnancy, planned pregnancy, unwillingness to use effective birth control during the trial or breast feeding
- Any other condition, which in the opinion of the investigator would impede compliance or hinder completion of the study
- Failure to give informed consent

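### Section 8.2 commits to excluding people with impaired hepatic function, but the listed hepatic criterion starts at ALT above 2xULN or Child-Pugh 10, and 8.2 does not refer to it

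*Combined protocol and SAP*

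**What the plan says.** Section 8.2, under the management of comorbid conditions, says that the Brochure "does not recommend use of the drug in patients with impaired hepatic or renal function". The next sentence draws the consequence: "Prospective participants with these conditions will be excluded from the trial". Neither sentence grades the impairment or cites 5.2.

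The exclusion list in 5.2, matched by the synopsis in 1.1, has one hepatic entry: "Significant hepatic injury as defined by alanine aminotransferase (ALT) elevation of greater than 2xULN or a Child-Pugh score of 10 or greater".

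It has two renal entries. One begins "Impaired renal function as defined by estimated glomerular filtration rate (eGFR" and sets the limit at eGFR below 60. The other is "History of chronic kidney disease or on hemodialysis or peritoneal dialysis".

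Two further entries in 5.2 rest on the investigator's opinion: "Another active disorder which could explain symptoms in the opinion of the investigator" and "Any other condition, which in the opinion of the investigator would impede compliance or hinder completion of the study".

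**The concern.** The protocol makes a safety commitment in one place and implements it more narrowly in another. For the kidney, the idea in 8.2 (impaired function) reappears in 5.2 under the same name, with a limit attached. For the liver, 5.2 substitutes a different and more severe idea, injury of a significant degree, and sets the Child-Pugh limb at 10. People with milder hepatic impairment fall between the two texts.

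At stake is whether a precaution that the protocol takes from the Brochure is applied before the first dose. Staff working from 8.2 would turn such a person away; staff working from 5.2 would find no hepatic reason to do so. Section 6.3 issues an assignment only when the trial database shows eligibility, and 8.1.2 describes a check run on keyed forms. If that check was built from 5.2, it would let the person through.

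**Working it through.** No figure in the plan needs to be reproduced. The check compares the texts and applies the listed rule.

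**1. The two texts side by side**

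| | Section 8.2 | Sections 1.1 and 5.2 |
|---|---|---|
| Renal | Impaired function excluded, no limit stated | eGFR below 60; history of chronic kidney disease, or dialysis (2 criteria) |
| Hepatic | Impaired function excluded, no limit stated | ALT above 2xULN or Child-Pugh 10 or more (1 criterion) |

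**2. Applying the hepatic rule.** A person is excluded if ALT > 2xULN or Child-Pugh ≥ 10. The complement is ALT ≤ 2xULN and Child-Pugh ≤ 9. Anyone in that complement who has hepatic impairment is covered by the words of 8.2 and by no hepatic entry in 5.2.

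**3. Other routes to exclusion before dosing.**
- The two opinion-based entries in 5.2 concern the cause of the symptoms, and compliance or completion. Neither concerns drug safety in liver impairment.
- The physician's case-by-case review in 6.5 concerns the medication profile.
- The screening metabolic panel in 1.3 has 14 analytes. Five are liver-related (albumin, total bilirubin, ALP, AST, ALT). Only ALT has its own limit in the hepatic criterion.
- The eligibility check in 8.1.2 exists, but its hepatic items are not described.

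**4. Safeguards after dosing.** Sections 7.1, 7.2 and 8.2 allow study drug to be stopped or a participant withdrawn on safety grounds, and 8.2 has an elevated ALT repeated within 5 days. The week 2 visit covers history, adverse events and vital signs. The metabolic panel is scheduled at screening, week 4 and week 6 (1.3), and 12.2 shows 0 mL of blood at week 2. The first scheduled liver tests after randomisation therefore fall at week 4, the end of treatment. The withdrawal rule in 7.2 for meeting an exclusion criterion relies on the same list.

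**5. What a lower cut-off would do.** The documents do not give the Child-Pugh range. Assume whole-number scores from 5 to 15. The number of scores left below a cut-off c is c − 5:

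| Cut-off | Scores left unexcluded |
|---|---|
| 10 (current) | 10 − 5 = 5 |
| 9 | 9 − 5 = 4 |
| 8 | 8 − 5 = 3 |
| 7 | 7 − 5 = 2 (scores 5 and 6) |

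Even at 7, some scores remain below the limit. Lowering the number narrows the gap, but only a reference from 8.2 to 5.2 closes it.

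**6. Scale.** The documents give no prevalence of mild or moderate hepatic impairment in this population. Per 1% of enrolment: 108 × 0.01 = 1.08 participants.

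**The case against.** The strongest reply is that 8.2 is background prose and 5.2 is the definition. On that view 8.2 announces exclusions for two organs and 5.2 says what they are, with entries for both. Nor do the texts collide in operation: 5.2 never obliges a site to enrol anyone. This reading is possible but strained. The renal entry in 5.2 keeps the term used in 8.2 and the hepatic entry does not, while 8.2 cites 6.5 in the same sentence as the Brochure warning and never cites 5.2.

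Other parts of the reply stand:
- Having a threshold is not the defect. The renal rule also leaves out people with slightly reduced function who have eGFR of 60 or more and no kidney history. A reader might infer that every limit in 5.2 breaches 8.2; taken that far, the argument would condemn the renal rule too, which is a reasonable way to define impairment.
- A cut-off of 7 would not by itself reconcile the texts, as step 5 shows.
- The value 7 has no support in the documents. The Brochure's severity limits are not given, so they cannot show which of the two texts is at fault.
- The ALT limb removes some affected people whatever their Child-Pugh score, and treatment lasts only 4 weeks.
- Uneven handling across the six sites is possible but not established, because eligibility is confirmed centrally.

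**Conclusion.** The mismatch holds as a minor safety-alignment point. Section 8.2 promises an exclusion for impaired hepatic function that the listed criterion delivers only at ALT above 2xULN or Child-Pugh 10 or more. No other pre-dosing rule in the documents fills the gap.

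A reader might go further and infer that Child-Pugh 10 is demonstrably unsafe, or that participants will be harmed. The documents do not support either. Section 6.1.1 notes extensive first-pass metabolism, but there are no exposure data by liver function. It is also not shown that such people will be randomised; that depends on how the eligibility check was built.

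The number affected is unknown and probably small, about 1 participant for each 1% of the planned enrolment. The sample size and the primary analysis do not change. The conclusion rests on reading the two sentences in 8.2 as written. The Child-Pugh range and the value 7 are assumptions that bear on the remedy; they do not affect whether the texts differ.

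**What to change.** Make two linked changes.

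1. In 1.1, 5.2 and the eligibility check, keep ALT above 2xULN and lower the Child-Pugh cut-off. A value of 7 or greater is assumed here and must be confirmed against the Brochure first.
2. In 8.2, state that hepatic and renal impairment are as defined in 5.2. Scores left below the new cut-off then no longer conflict with 8.2.

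If the Brochure confines its warning to severe impairment, leave the cut-off at 10 and correct only the wording of 8.2.

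The cost is one criterion edited in two places, one cross-reference and one edit to the eligibility check. Child-Pugh is already part of the criterion, so the lower cut-off calls for no measurement that the current rule does not. The downside is possibly a few more screen failures.
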